Pain intensity in the affected shoulder over the past 7 days, assessed separately in three specific contexts:

- Maximum pain experienced
- Pain during physical activity
- Pain at rest

Endpoint:

Each pain domain is measured on a 100 mm visual analogue scale (VAS) anchored with 0 = “No pain” and 100 = “Worst pain imaginable,” as recommended by the OARSI.³⁶ The key secondary endpoint is the between-group difference in change from allocation to 1 year follow-up. Additional measurements will be collected at 3 and 6 months.

4. Shoulder-Related Sleep Disturbance

Outcome:

Degree of sleep disturbance attributed to shoulder symptoms in the past 7 days.

Endpoint:

Measured using a 100 mm VAS, anchored with 0 = “Not disturbed” and 100 = “Extremely disturbed.” The key secondary endpoint is the between-group difference in change from allocation to 1 year follow-up, with additional measurements at 3 and 6 months.

Covariates for development of propensity score

To account for potential confounding and to improve comparability between the surgical and non-surgical treatment cohorts, propensity score adjustment will be applied. The propensity

score will be estimated as the conditional probability of receiving surgical treatment, given a set of baseline covariates measured prior to treatment allocation.

Covariates are selected based on clinical relevance and their potential association with both treatment assignment and outcomes. These include patient-reported measures of general health, health-related quality of life, fear-avoidance beliefs, treatment expectations, and physical activity levels, as well as sociodemographic characteristics (e.g., age, sex, education), lifestyle factors (e.g., smoking, BMI), and clinical assessments including imaging and physical examination findings.

All covariates used in the propensity score model were collected prior to referral to either surgical or non-surgical treatment pathways. The full list of covariates and the timing of their assessment, along with the timing of primary and secondary outcome measurements, is detailed in Box 1.

Box 1: Outcome and Covariates – Timepoint of assessment.

	Timepoint of assessment			
	Baseline	3 months	6 months	1 year
Outcome measures				
Primary outcome				
PASS, no. (%)				X
Quick-DASH MIC, no. (%)				x
Key Secondary Outcomes				
GPE - Overall shoulder problems - no. (%)				X
Quick-DASH - 0-100	X	X	X	X
VAS shoulder pain 'Maximum' - 0-100	X	X	X	X
VAS shoulder pain 'Activity' - 0-100	X	X	X	X

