The primary analyses will be based on the Intention to Treat (ITT) population. Categorical endpoints (e.g., the proportion achieving PASS/Quick-DASH MIC after 1 year) will be analysed using logistic regression, with treatment group and stratification factors as covariates, based on the IPW data provided initially. The primary estimand will be the odds ratio (OR) with 95% confidence intervals (CIs) derived from the fully adjusted logistic regression model. The main analysis will use inverse probability weighting, with further adjustment for stratification variables. The OR will represent the treatment effect, with CIs providing the range within which the true treatment effect is expected to lie with 95% certainty. A p-value will be reported to assess the statistical significance of the treatment effect, testing the null hypothesis of no difference between groups. An OR >1 indicates higher odds of achieving the PASS/Quick-DASH MIC outcome with surgical treatment, while an OR <1 indicates lower odds. For secondary objectives, categorical outcomes will be analysed using the same approach as the primary endpoints, while continuous outcomes will be analysed as change from baseline using repeated-measures mixed-effects linear models. Patient identification number will be included as a random effect. Fixed effect factors will include baseline score, treatment group (Shoulder Surgery vs Nonoperative Treatment), time point (baseline, 3, 6, and 12 months), stabilised inverse probability of treatment weighting (sIPTW), and treatment-by-time interactions.

Sensitivity analysis will be performed with the purpose to test the robustness of the primary analyses, based on the per-protocol population, if $>5\%$ of the total number of patients in one treatment group are major protocol violators. The per-protocol analysis set will include: 1) patients who in the surgical group were 'allocated (initial clinical decision at first medical examination) to receive surgery, and have a record of the surgery was performed in the REDCap database, including date and type of surgery performed, 2) patient who in the non-surgical group were allocated (initial clinical decision at first medical examination) to receive non-surgical treatment and a minimum of 1 record, in the REDCap database, of receiving non-surgical intervention after the initial clinical examination as well as no record of surgery performed.

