Subgroup analyses will be performed if imbalance is seen in the applied stratification sequence, only including diagnostic subgroups with balanced patient distributions between surgical treated patients and non-surgical treated patients.

Missing data

Missing data are ignorable only when they are missing completely at random (MCAR), meaning no systematic differences exist between missing and observed values. More commonly, data are assumed to be missing at random (MAR), where any systematic

differences can be explained by observed variables.²⁷ Under the MAR assumption, repeated measures mixed-effects models or multiple imputation is recommended as it yields valid standard errors, P values, and confidence intervals.⁴⁶ For categorical efficacy endpoints, missing data at 1 year from baseline will be addressed through non-responder imputation, which is supposedly representing a conservative approach. For continuous efficacy endpoints repeated measures mixed effects models will handle missing data; missing data will be handled indirectly with the use of the mixed-effects linear-models approach with an assumption that data were missing at random, in accordance with the working assumption underlying these models.⁴⁷

Additional analyses

No additional analyses are planned.

Harms

No data on harm was collected.

Statistical software

All statistical analyses will be conducted using SAS (SAS Institute Inc) and R (R Foundation for Statistical Computing). SAS will be used primarily for data management and modeling, while R will be applied for supplementary analyses, data visualisation, and reproducibility checks.

REFERENCES:

1. Lucas J, van Doorn P, Hegedus E, et al. A systematic review of the global prevalence and incidence of shoulder pain. *BMC Musculoskelet Disord* 2022;23(1):1073. doi: 10.1186/s12891-022-05973-8 [published Online First: 2022/12/09]

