Morphine or opioids — no. (%)

Other — no. (%)

Diagnostic group

Degenerative — no. (%)

Non-Specific shoulder pain — no. (%)

Non-traumatic instability/luxation — no. (%)

Traumatic injury — no. (%)

Quick-DASH score‡ — 0 to 100

VAS Shoulder pain Maximum§ — 0 to 100

VAS Shoulder pain Activity§ — 0 to 100

VAS Shoulder pain Rest§ — 0 to 100

VAS Shoulder related sleep

Disturbance§ — 0 to 100

* Plus-minus values are mean \pm SD unless otherwise indicated.† The Danish Health Authority guideline recommends alcohol consumption lower than 7 units per week for females and 14 units per week for males to have a low risk of developing diseases.⁴⁸

‡ The short version of the Disability of the Arm, Shoulder and Hand Questionnaire (Quick-DASH) ranges from 0 to 100, with higher scores indicating worse disease status.

§ Visual Analog Scale (VAS) ranges from 0 to 100, with higher scores indicating worse status.

Table 2. Primary and Key Secondary Outcomes at 1 year in the Intention-to-Treat Population.*

VARIABLE	SURGICAL GROUP	NON-SURGICAL GROUP		BETWEEN GROUP	
		OR (95%CI)		Crude	Adj.
PRIMARY OUTCOME					
PASS - no. (%)					
QUICK-DASH MIC - no. (%)					
KEY SECONDARY OUTCOME					
GPE - OVERALL SHOULDER PROBLEMS - no. (%)					

	Mean change from baseline	SE	Mean change from baseline	SE	LSMean difference (95% CI)	
					Adj.	p-value
Quick-DASH - 0 to 100						
VAS SHOULDER PAIN MAXIMUM - 0 to 100						
VAS SHOULDER PAIN ACTIVITY - 0 to 100						
VAS SHOULDER PAIN REST - 0 to 100						
VAS SLEEP DISTURBANCE - 0 to 100						

PASS: Patient Acceptable Symptom State; GPE: Global Perceived Effect; Quick-DASH: Short form of Disability of the Arm, Shoulder and Hand questionnaire; VAS: Visual Analog Scale. * All analyses will be based on the ITT population: For dichotomous outcomes, logistic regression will be applied, with treatment group and stratification factors as covariates, based on the IPW data (missing data at 1 year from allocation will be addressed through non-responder imputation); The primary estimate will be the odds ratio (OR) with 95% confidence intervals (CIs) derived from the logistic regression model. For continuous outcomes, repeated measures linear mixed effects models (with no imputation for missing data) will be applied; Estimates are mean change from baseline and standard deviations with difference between groups reported with 95% confidence intervals.

Figures:

[figure not shown]

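### For the five continuous secondary outcomes, the missing-at-random assumption rests on a model without the Box 1 covariates, so loss that depends on them differently by arm would bias the 1-year differences, probably modestly

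*SAP*

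**What the plan says.** The Missing data section describes data as missing at random when systematic "differences can be explained by observed variables". It then handles the categorical endpoints by non-responder imputation, which keeps every patient. For the continuous endpoints (items 4 to 8 of the testing hierarchy), "missing data will be handled indirectly with the use of the mixed-effects linear-models approach with an assumption that data were missing at random". The footnote to Table 2 confirms that "repeated measures linear mixed effects models (with no imputation for missing data) will be applied".

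The model is set out under Analysis methods: "Fixed effect factors will include baseline score, treatment group (Shoulder Surgery vs Nonoperative Treatment" and, continuing the same list, "time point (baseline, 3, 6, and 12 months), stabilised inverse probability of treatment weighting (sIPTW), and treatment-by-time interactions". Also, "Patient identification number will be included as a random effect". No Box 1 covariate appears in its own right.

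Those covariates are used in the propensity score. The section on covariates for that score says "Covariates are selected based on clinical relevance and their potential association with both treatment assignment and outcomes". The score itself is defined as the probability of being in the surgical group. Nothing in the SAP models the probability of still replying at 1 year.

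The only sensitivity analysis is a per-protocol one, done only if major deviations exceed 5% in a group. The Additional analyses section plans nothing further.

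**The concern.** A likelihood-based mixed model without imputation is valid under missing at random only given the variables it conditions on. The SAP justifies the assumption by appeal to observed variables, then leaves most of the observed variables out of the model.

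The weights do not close the gap. They are built on everyone allocated and aim at balance at that moment. A patient with no follow-up score adds no outcome information to items 4 to 8. If, say, patients with poor well-being drop out of the non-surgical arm but not of the surgical arm, those observed at 1 year are no longer comparable, however good the weights were at the start. This is attrition (selection) bias.

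Five of the eight hierarchy items use this model. The same intervals will also be read against the 10-point margin for absence of an important difference, so a systematic shift matters for that reading too. The SAP's own introduction acknowledges that uneven loss can bias a trial.

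**Working it through.** **Inputs from the SAP.** Total 992 at 1:15, so 992/16 = 62 surgical and 62 × 15 = 930 non-surgical. The stated 92% power for 0.80 v 0.60 reproduces (0.920, normal approximation with pooled null variance). That figure fixes the group sizes and has no bearing on missing data. The threshold for items 4 to 8 is 10 points. The SAP gives no expected loss, no SD and no covariate effect, so everything below rests on assumptions.

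**Approximate size.** Let β be the covariate's effect on the 1-year score per SD, and d the weighted difference between arms in the covariate's mean (in SD) among patients observed at 1 year. Then bias ≈ β × d, less whatever the earlier scores recover.

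**Simulation with sIPTW as a weight.** 300,000 patients per scenario, about 1:15, true 1-year difference 0. One measured covariate X drives allocation and outcome, with β = 8 points per SD. 12 to 43% of 1-year scores are missing per arm in the scenarios with loss. In every scenario X was balanced at allocation (difference about 0 SD).

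| How loss depends on X | d at 1 year (SD) | Error in 1-year difference (points) |
|---|---|---|
| No loss, or loss depending on arm only | about 0 | −0.4 to +0.3 |
| Same relation in both arms, constant treatment effect | 0.01 | 0.0 to +0.2 |
| Same relation, treatment effect varies by 5 points per SD | −0.02 to −0.03 | −0.7 to −1.5 |
| Related to X in the non-surgical arm only | 0.24 to 0.26 | +1.5 to +2.2 |
| Related to X in opposite directions by arm | 0.47 to 0.50 | +2.8 to +4.8 |

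The formula agrees with this. Take the runs with a constant treatment effect in which leavers gave no follow-up score. One-arm loss: 8 × 0.239 = 1.9, simulated +1.86. Opposite loss: 8 × 0.497 = 4.0, simulated +4.08. When leavers dropped out at different visits, 8 × 0.258 = 2.1 against +1.62 simulated, and 8 × 0.466 = 3.7 against +2.77. Earlier scores recover part of the error.

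**Milder inputs.** Unweighted analysis of an index already balanced at allocation, worth 5 to 8 points per SD; patient SD 13, residual SD 14. Replies are 80 to 90% (surgical, unrelated to the index) and 60 to 80% (non-surgical, odds of reply falling 1.5- to 2.5-fold per SD). Half of the 1-year non-responders answered earlier. Bias is about 0.25 to 1.3 points. A further simulation with sIPTW as a weight gave about −0.1 when loss was the same in both arms and +1.0 to +2.4 when it differed.

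**Which remedy works.** 600,000 patients per scenario, sIPTW as a weight, true effect 0, simulation noise about ±0.3 points:

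| Loss related to covariate | Its effect at 3, 6, 12 months | As planned | Main effect added | Covariate-by-time added |
|---|---|---|---|---|
| Non-surgical arm only | constant | +0.8 | −0.2 | not needed |
| Non-surgical arm only | 3, 5, 8 points | +1.4 | +0.8 | +0.1 |
| Opposite directions | 3, 5, 8 points | +1.9 | +1.0 | +0.2 |

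A main effect is enough only if the covariate acts equally at every visit. In the 300,000-patient simulation, sIPTW multiplied by correctly specified inverse-probability-of-remaining weights brought the arm-differential errors to between −0.3 and +0.7.

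**Precision.** At 62 v 930 in a middle case of the milder set (8 points per SD, odds ratio 2, replies 85% v 70%), adding the index cut the SE from 2.90 to 2.71. The variance saving is 1 − (2.71/2.90)² = 13%. This was shown for an unweighted analysis of one index, so it is indicative only.

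**The case against.** The strongest case against is about size and convention. A mixed model under an openly stated missing-at-random assumption is standard practice. The outcomes are secondary and support claims only if PASS, Quick-DASH MIC and GPE are all significant first. Under the milder inputs the bias is less than half its SE (1.3/2.90 = 0.45). Nothing in the SAP suggests that loss will differ by arm. All of this stands and keeps the point at a low grade. It does not remove it, because no planned analysis would correct or reveal the bias.

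Four stronger readings are tempting, and the document does not support them.

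- A reader might infer that any covariate-related loss reopens confounding and biases all five differences. It does not. With the same relation in both arms and no effect variation the error was 0.0 to +0.2. Where bias arises it is attrition bias, not confounding of allocation.
- A reader might infer that the model conditions on nothing beyond baseline score, arm and earlier scores. The SAP also lists sIPTW, a function of arm and the Box 1 covariates. It does not cure the problem: used both as a weight and as a covariate, arm-differential loss still gave +2.7 to +6.6.
- A reader might take the intention-to-treat label in Table 2 as contradicted by patients without follow-up. That is ordinary usage of the term.
- A reader might expect covariate main effects to be a full repair. The second table shows otherwise.

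**Conclusion.** The point holds in conditional form. For items 4 to 8 the missing-at-random assumption is tied to a model that omits the individual Box 1 covariates, and the weights address allocation only. Loss that depends on a prognostic covariate differently by arm would therefore bias the 1-year differences. With sIPTW used as a weight and the assumed inputs above (5 to 8 points per SD, 10 to 40% loss), the bias is roughly 0.25 to 2.5 points, and up to about 5 when loss runs in opposite directions and the treatment effect also varies with the covariate. Every figure is below 10 points. None can be pinned down from the SAP, which states no loss rates.

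Grade: consider. The outcomes are secondary and the likely bias is modest.

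Listing sIPTW as a fixed effect is a separate and larger matter. Used only as a covariate, it left an error of about 5.7 points even with no loss, the same as the crude analysis.

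**What to change.** **Analysis methods.** For items 4 to 8, apply sIPTW as a weight rather than as a fixed effect. Add a short prespecified list of Box 1 covariates expected to predict both reply and outcome, each with a covariate-by-time term. Candidates are age, sex, education, work status, symptom duration, treatment preference, expectation, WHO-5 and number of pain sites; the final choice is the sponsor's.

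**Missing data.** State that missing at random is assumed given these covariates and the earlier scores. As a check, report the 1-year difference from multiple imputation done separately by arm, using the same covariates and the 3- and 6-month scores. Weighting by sIPTW multiplied by inverse-probability-of-remaining weights would serve instead. Either check can also address loss combined with an effect that varies by covariate, which covariate-by-time terms common to both arms do not.

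**Cost.** SAP wording and a little programming. Ten to fifteen coefficients at each of three visits make 30 to 45, affordable in a linear model on about 990 patients. The list must stay short for imputation by arm: at an assumed 85% reply, 62 surgical patients give about 53 observed 1-year scores (0.85 × 62 = 52.7). Missing covariate values will need imputing.

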

48. Danish Health Authority. Sundhedsstyrelsens udmeldinger om alkohol 2021 [Available from: <https://www.sst.dk/da/viden/alkohol/alkoholforebyggelse/sundhedsstyrelsens-udmeldinger-om-alkohol> accessed 14-05-2021.

Tables:**Table 1. Baseline Characteristics of the Patients in the ITT population. ***

	Surgical group (N=??)	Non-Surgical group (N=??)	Between-Group Differences (95% CI)	Standardised Differences
Female sex — no. (%)				
Age — yr				
Height — m				
Weight — kg				
Body-mass index — kg/m ²				
Education level beyond high school — no. (%)				
Employment				
Employed for wages — no. (%)				
Self-employed — no. (%)				
Unemployed — no. (%)				
Sick leave — no. (%)				
Retired — no. (%)				
Other — no. (%)				
Substance use				
Current smoker — no. (%)				
Alcohol consumption above recommendations† — no. (%)				
Index shoulder right — no. (%)				
Duration of shoulder symptoms — months				
Previous treatment for current shoulder disorder				
Physiotherapist/Chiropractor — no. (%)				
Corticosteroid injection — no. (%)				
Used pain medication in the past week due to shoulder-related pain				
Paracetamol — no. (%)				

Ibuprofen — no. (%)

Morphine or opioids — no. (%)

Other — no. (%)

Diagnostic group

Degenerative — no. (%)

Non-Specific shoulder pain — no. (%)

Non-traumatic instability/luxation — no. (%)

Traumatic injury — no. (%)

Quick-DASH score‡ — 0 to 100

VAS Shoulder pain Maximum§ — 0 to 100

VAS Shoulder pain Activity§ — 0 to 100

VAS Shoulder pain Rest§ — 0 to 100

VAS Shoulder related sleep

Disturbance§ — 0 to 100

* Plus-minus values are mean \pm SD unless otherwise indicated.† The Danish Health Authority guideline recommends alcohol consumption lower than 7 units per week for females and 14 units per week for males to have a low risk of developing diseases.⁴⁸

‡ The short version of the Disability of the Arm, Shoulder and Hand Questionnaire (Quick-DASH) ranges from 0 to 100, with higher scores indicating worse disease status.

§ Visual Analog Scale (VAS) ranges from 0 to 100, with higher scores indicating worse status.

Table 2. Primary and Key Secondary Outcomes at 1 year in the Intention-to-Treat Population.*

VARIABLE	SURGICAL GROUP	NON-SURGICAL GROUP		BETWEEN GROUP	
		OR (95%CI)		Crude	Adj.
PRIMARY OUTCOME					
PASS - no. (%)					
QUICK-DASH MIC - no. (%)					
KEY SECONDARY OUTCOME					
GPE - OVERALL SHOULDER PROBLEMS - no. (%)					

	Mean change from baseline	SE	Mean change from baseline	SE	LSMean difference (95% CI)	
					Adj.	p-value
Quick-DASH - 0 to 100						
VAS SHOULDER PAIN MAXIMUM - 0 to 100						
VAS SHOULDER PAIN ACTIVITY - 0 to 100						
VAS SHOULDER PAIN REST - 0 to 100						
VAS SLEEP DISTURBANCE - 0 to 100						

PASS: Patient Acceptable Symptom State; GPE: Global Perceived Effect; Quick-DASH: Short form of Disability of the Arm, Shoulder and Hand questionnaire; VAS: Visual Analog Scale. * All analyses will be based on the ITT population: For dichotomous outcomes, logistic regression will be applied, with treatment group and stratification factors as covariates, based on the IPW data (missing data at 1 year from allocation will be addressed through non-responder imputation); The primary estimate will be the odds ratio (OR) with 95% confidence intervals (CIs) derived from the logistic regression model. For continuous outcomes, repeated measures linear mixed effects models (with no imputation for missing data) will be applied; Estimates are mean change from baseline and standard deviations with difference between groups reported with 95% confidence intervals.

Figures:

[figure not shown]

Figure 1: CONSORT flow-chart. Surgical group (Intervention), Non-Surgical group (Comparator)
